15.2 Power Analysis

A total of 30 completed participants will achieve >80% power, for each of the two primary outcomes (satisfaction and crossover point), to detect two sugar conditions (high vs. low)’ difference of a moderate effect size ($d = 0.6$, the target scenario) at a 0.025 (= 0.05/2 primary outcomes) significance level, assuming a moderate correlation between sessions ($r = 0.50$) based on a T^2 test using PASS14 (NLSS, 2015). A total of up to 75 eligible smokers will be enrolled..

We note that because of the uncertainty of the effects of sugars and the range of effect sizes, we chose an effect size that is more conservative but near the range of the effect sizes (based on the endpoint of crossover point from the Multiple Choice Procedure task) used in most studies. The powers of the target scenario and other scenarios by changing the within-subject correlation and effect size, with the fixed sample size ($n = 30$) and type I error ($\alpha = 0.025$), are presented in the table below. We note that the actual power for the factor of sugar level could be larger since 3 sugar levels will be studied.

Scenario	Power	Effect size (d)	Within-subject correlation (r)
Target scenario	0.81	0.6	0.5
	0.89	0.6	0.6
	0.64	0.5	0.5

Other scenarios	0.75	0.5	0.6
	0.92	0.7	0.5
	0.96	0.7	0.6

15.3 Statistical Analysis

General Approach

All statistical analyses will be performed using SAS or R. All statistical tests will be two-tailed. A Bonferroni adjustment will be used to account for 2 primary endpoints ($p < 0.025$ considered significant). Analyses of the secondary endpoints will not be adjusted ($p < 0.05$ considered significant). Proper transformation such as the logarithm transformation will be used to approximate normality for the outcome variables.

Describing the Study Population

Baseline characteristics of the participants will be summarized using mean and standard deviation (SD) for continuous variables and frequency and percentage for categorical variables.

Primary Analysis

The primary data analysis method will be linear mixed models including the two within-subject factors, sugar condition (2 dummy variables for the medium and high sugar levels) and time (2 dummies for the 3rd and 4th sessions), adjusted for the nicotine levels in spent filters of the first study cigarette used in each of the laboratory sessions (under the fixed puffing pattern). The potential carry-over effect will be tested by including the previous session's condition, i.e., 2 dummies for the previous session being medium and high sugar level (Diggle et al., 2002, p150-153). Note that the usual brand's measure (collected at the 1st session) and other participant-level factors are naturally adjusted across different sugar conditions because of the within-subject design, and hence are not included in the model. However, participant-level factors will be examined for any potential moderating effect (i.e., interaction) as an exploratory analysis.

Subgroup Analysis

Subgroup analyses will be performed for female and male smokers. The analyses will follow the same approach described for the overall group. Note that this study is not powered for detecting the potential interaction of gender and sugar level, however, we will report the size and significance of the interaction together with the subgroup analysis results to provide information for understanding of the role of gender.

Missing data

Every effort will be made to limit the amount of missing data in this trial, and study participants will be incentivized to attend study sessions. We anticipate a high retention rate (>80%) because of the short period of time of this laboratory study.

We will compare subjects who do and do not complete the study sessions in terms of their baseline characteristics. All observed data will be utilized in the analyses, with missing data being assumed to be missing at random, by using the mixed effects models.

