15.0 Statistical Considerations

15.1 Data Analysis Plan

Trial design

The aim of this study is investigate the impact of sugar content in cigarette tobacco on cigarette abuse liability and appeal. The hypothesis is that the collected measures will indicate lower abuse liability for cigarettes with lowest sugar content.

This is a within-subject crossover study design with multiple periods and multiple treatments. The orders of the 3 sugar levels are counterbalanced using a Latin square, which will be created in advance by an independent statistician.

Trial endpoints

Outcome measures include subjective responses to cigarettes, behavioral measures, and mouth-level nicotine exposure.

Two *primary* outcome measures, which were used for power/sample size determination, include (1) the satisfaction of the Modified Cigarette Evaluation Questionnaire (mCEQ) and (2) the crossover point from the Multiple Choice Procedure task.

The other subjective and behavioral outcomes and mouth-level nicotine exposure will be *secondary*.

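### Plain Bonferroni across the two primary endpoints is valid but gives up power that 5% family-wise control does not require; Holm's step-down would be a cheap improvement

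*Combined protocol and SAP*

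**What the plan says.** Section 15.1 says that the primary outcome measures "include (1) the satisfaction of the Modified Cigarette Evaluation Questionnaire (mCEQ) and (2) the crossover point from the Multiple Choice Procedure task". Section 15.3 (General Approach) sets the multiplicity rule: "A Bonferroni adjustment will be used to account for 2 primary endpoints", with significance at p < 0.025. It adds: "All statistical tests will be two-tailed".

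Section 15.2 sizes the trial at the same level: "A total of 30 completed participants will achieve >80% power" for each primary outcome, "at a 0.025 (= 0.05/2 primary outcomes) significance level". The target is a high-versus-low difference of d = 0.6 with a between-session correlation of 0.50, and the table gives power 0.81 for it.

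No section describes a step-down rule or any other way of passing alpha from one endpoint to the other. The documents do not say whether success means either endpoint or both, and they give no correlation between the two endpoints.

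**The concern.** Single-step Bonferroni holds each endpoint to 0.025 even after the other has been established. If satisfaction gave p = 0.004 and the crossover point p = 0.03, the crossover point would be declared negative. Control of the family-wise error at 5% does not require that. Once one null hypothesis has been rejected at 0.025, Holm tests the remaining one at 0.05. It keeps the 5% guarantee under any dependence between the endpoints, and it needs no ordering of endpoints and no assumption about their correlation.

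At stake is the ability to make a second, separate claim. That matters in a study with 30 completers and 0.81 power per endpoint at the target, and only 0.64 in the plan's own d = 0.5, r = 0.5 scenario.

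**Working it through.** **Inputs.** From section 15.2: n = 30 completers, d = 0.6 for high versus low, r = 0.50, alpha = 0.025 per endpoint. From section 15.3: two-sided tests. The correlation between the two endpoints' within-person differences (rho) is not in the documents; it is assumed, and a range of 0 to 0.9 is shown.

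**Step 1: reproduce the plan's figure.** Section 15.2 describes the calculation as "based on a T^2 test using PASS14 (NLSS, 2015". For a single high-low contrast, T² is equivalent to the paired t test.
- Standardised difference: dz = d / √(2(1 − r)) = 0.6 / √1 = 0.6.
- Noncentrality: 0.6 × √30 = 3.286, with 29 df.
- Power: 0.816 at two-sided 0.025 (plan: 0.81) and 0.888 at two-sided 0.05.

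The six rows of the table come out at 0.816, 0.898, 0.647, 0.754, 0.923 and 0.968, against 0.81, 0.89, 0.64, 0.75, 0.92 and 0.96 in the plan. All agree within 1 point.

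**Step 2: the two rules.**
- Bonferroni: endpoint i is significant if pᵢ < 0.025.
- Holm: endpoint i is significant if pᵢ < 0.025, or if pᵢ < 0.05 and the other endpoint has p < 0.025.

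The gain per endpoint is therefore the probability that its p lies between 0.025 and 0.05 while the other p is below 0.025.

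**Step 3: check by hand at rho = 0.**
- Holm, per endpoint: 0.816 + (0.888 − 0.816) × 0.816 = 0.875.
- Bonferroni, both: 0.816² = 0.666.
- Holm, both: 0.888² − (0.888 − 0.816)² = 0.783.

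**Step 4: simulation over rho.** Two correlated paired t statistics, 1,000,000 draws per row, d = 0.6 on both endpoints:

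| rho | Per endpoint: Bonferroni | Per endpoint: Holm | Gain (points) | Both: Bonferroni | Both: Holm | Gain (points) |
|---|---|---|---|---|---|---|
| 0 | 0.816 | 0.876 | 5.9 | 0.667 | 0.784 | 11.7 |
| 0.3 | 0.816 | 0.870 | 5.3 | 0.688 | 0.794 | 10.6 |
| 0.5 | 0.816 | 0.864 | 4.9 | 0.707 | 0.804 | 9.7 |
| 0.7 | 0.816 | 0.860 | 4.4 | 0.731 | 0.818 | 8.7 |

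At rho = 0.8 the gains are 3.9 and 7.9 points, and at rho = 0.9 they are 3.4 and 6.7 points.

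**Step 5: other effect patterns.**
- d = 0.6 on one endpoint and 0.5 on the other, rho = 0.3: power for the weaker endpoint goes from 0.647 to 0.731.
- d = 0.6 on one endpoint and no effect on the other: the real effect gains 0.1 to 0.2 points.
- The plan's other five table scenarios, rho 0 to 0.9: gains of 1.0 to 6.9 points per endpoint and 2.0 to 13.8 points for both.
- At least one significant endpoint: identical under the two rules in every scenario, because both need the smaller p to be below 0.025.

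**Step 6: error rates.** With both nulls true, the family-wise error is the same under either rule: 0.049, 0.047 and 0.040 at rho = 0, 0.5 and 0.8. With one null true, Holm's false-positive rate for it is 0.040 to 0.045, below 0.05. Bonferroni's is about 0.025.

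**The case against.** The case for leaving section 15.3 alone is respectable. Bonferroni controls the error rate, sections 15.2 and 15.3 agree on 0.025, and the stated power is met under the rule actually planned. A reader might infer from the calculations that the trial is underpowered or its multiplicity control faulty. The documents support neither reading.

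A reader might also take gains of roughly 5 points per endpoint and 9 to 12 points for both as what the plan loses outright. They are conditional on real target-size effects on both endpoints and on a correlation that the documents do not report. The two measures concern the same cigarette in the same session, so a high correlation is possible. Section 15.2 itself stresses uncertainty about the effects of sugar and refers its effect size to the crossover point only.

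The figure for both endpoints needs care too. If success required both, each could be tested at 0.05 with no adjustment. If either suffices, Holm adds nothing to the chance of success. The real benefit is a second claim, and the stated hypothesis about the collected measures gives that claim some value.

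Two practical objections stand. First, every additional Holm rejection has p between 0.025 and 0.05, so the matching 97.5% interval includes zero in exactly those cases; presenting such intervals without explanation would contradict the test. Second, Holm needs one p-value per endpoint. Section 15.3 fits medium and high dummies without naming the deciding test, and section 3.1 describes the primary outcome more broadly than section 15.1. Those gaps affect Bonferroni equally, but they have to be closed for either rule to deliver its guarantee.

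None of this makes Holm less powerful than Bonferroni in any scenario.

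**Conclusion.** The point holds as an efficiency improvement. With 30 completers, d = 0.6 on both endpoints, r = 0.5 and an assumed endpoint correlation of 0 to 0.7, Holm adds 4.4 to 5.9 points of power per endpoint and 8.7 to 11.7 points for showing both, at the same 5% family-wise level. The benefit shrinks as the correlation rises and nearly vanishes when only one endpoint responds.

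The power figures describe the paired high-low comparison that section 15.2 uses. The primary analysis is a mixed model adjusted for nicotine in the spent filters and using all observed data, and the gains under it may differ. The error guarantee and the fact that Holm never rejects less do not depend on the power model, provided each endpoint's p-value is valid.

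**What to change.** Before unblinding, replace the Bonferroni sentence in section 15.3 with Holm's step-down across the two primary endpoints named in section 15.1. Apply it to one two-sided p-value per endpoint, from the high-versus-low contrast that section 15.2 powers: the smaller p must be below 0.025 and, if it is, the other is tested at 0.05. Name that contrast in section 15.3 as the deciding test. Keep the calculation in section 15.2 and label it the conservative planning figure.

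Report Holm-adjusted p-values with unadjusted 95% intervals labelled as such. If 97.5% intervals are also shown, state that they are single-step intervals and can include zero when Holm rejects at p between 0.025 and 0.05.

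The cost is a few sentences of SAP text, with no change to sample size, data or procedures. The one real drawback is that intervals matching Holm are less simple than Bonferroni intervals, which the labelling above makes explicit.

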3.0 Study Endpoints/Events/Outcomes

3.1 Primary Endpoint/Event/Outcome

To evaluate the impact of sugar content on smoking intensity (nicotine levels in spent filters), subjective responses to cigarettes (e.g., reinforcing and sensory effects) and behavioral measures (multiple choice procedure, cigarette purchase task). We hypothesize that the collected measures will indicate lower abuse liability for cigarettes with lowest sugar content.

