5.0 Procedures Involved

5.1 Study Design

Overview: Participants (N=30 completers) will complete a baseline visit where they will smoke their usual brand cigarette. In the next three sessions, they will receive one of three study cigarettes with varying sugar content (low, medium and high) in a double-blind manner and counterbalanced order across participants. In each session, participants will first smoke either their usual brand cigarettes (at baseline) or their assigned study cigarette (subsequent sessions) in a regimented manner: 10 puffs total, 30 seconds between puffs. There will be a one-hour interval since the time of cigarette extinction before smoking the next cigarette. After this interval, participants will smoke their assigned cigarette *ad libitum* within a 10 minute time period. Safety and subjective measures will take place during this session as described below.

Anticipating a 60-65% attrition rate based on current experiences, we will recruit up to 75 participants.

Study Procedures: Smokers who smoke at least 5 cigarettes/day will attend 4 laboratory sessions during which they will be asked to smoke their usual brand (UB) cigarettes and then one of three study cigarettes with low, medium and high levels of sugar in separate sessions using a within-subject design with conditions counterbalanced determined by a Latin square. In each session, smokers will be asked to smoke a cigarette in a standardized manner (10 puffs, 30 second interval between puffs) and 1 hour later, *ad libitum*. Each of the sessions will be separated by at least 48 hours but not more than 5 days. The proposed study design has been used to assess the abuse liability of electronic cigarettes compared to other tobacco/nicotine products,⁹⁹⁻¹⁰¹ that vary in flavors and modified risk claims,¹⁰² and that vary in menthol

MEDICAL PROTOCOL (HRP-590)

[figure not shown]
PROTOCOL TITLE: Sugars Project

VERSION DATE: 22 FEB 2023

concentration and nicotine dose.¹⁰³ This design is also being utilized to determine the abuse liability of flavored cigar products.¹⁰⁴

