The first session for all participants will involve smoking their UB cigarettes. Participants will be asked to refrain from smoking for at least 12 hours prior to each session and must have alveolar CO ≤ 10 ppm to qualify for the session. Subsequently, the IVR records will be examined and vitals (blood pressure and heart rate) will be assessed through an automated cuff to ensure that eligibility criteria are still met. After a 30-minute rest period, participants will complete the MNWS, submit an alveolar CO sample, and will smoke their UB cigarettes in a regimented manner (10 puffs total, 30 seconds between puffs). Five minutes after extinguishing the cigarette, another CO measurement will be taken and participants will be asked to complete the mCEQ, Drug Effects/Liking Questionnaire, MNWS, QSU and Sensory Effects of Smoking Questionnaire, in a specified order via REDCap. The spent cigarette filter will be collected for nicotine analysis. There will be a one- hour interval since the time of cigarette extinction before smoking the next cigarette. During the intervening times between cigarettes, smokers will be allowed to read magazines, listen to neutral podcasts, or watch neutral videos. After this interval, participants will submit another CO, complete the MNWS and smoke their UB cigarettes *ad libitum* within a 10-minute timeframe and the same testing procedures will be followed. Twenty minutes after the second cigarette, the Perceived Health Risk Questionnaire will be administered and then at 30 minutes the Cigarette Purchase Task and Multiple Choice Procedures for the UB cigarettes will be administered. At 50 minutes (2 hours after smoking the first cigarette), participants will be asked to rinse their mouths and oral cells will be collected. At the very end of the session, the Willingness to Switch questionnaire will be administered. Once the Willingness to Switch questionnaire has been completed a number will randomly be selected from the Multiple Choice Procedures task. This will be done by pulling a number 1- 16 out of a jar. The participants will receive either an additional cigarette or the money associated with that number, depending on which choice was made for that number. The participant may choose to smoke the cigarette or not.

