In the next three sessions, participants will then be asked to smoke one of three study cigarettes with varying sugar content in a double-blind and counterbalanced order across participant s. Each study cigarette type will be labeled with a symbol (diamond, square or star to minimize ranking bias). Blinding of the cigarettes will occur in [name] laboratory, where staff do not have contact with participants. The same procedures as implemented with UB cigarettes will be followed.

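### The only primary model adjusts for filter nicotine from the assigned cigarette in the same session, so its sugar coefficient may not be the overall effect the trial aims to estimate

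*Combined protocol and SAP*

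**What the plan says.** Section 15.1 states the aim as to "investigate the impact of sugar content in cigarette tobacco on cigarette abuse liability and appeal". It names two primary outcomes: mCEQ satisfaction and the Multiple Choice Procedure crossover point.

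Section 15.3 gives one primary model for them. It is a linear mixed model with two dummies for sugar level and two for session, "adjusted for the nicotine levels in spent filters of the first study cigarette used in each of the laboratory sessions (under the fixed puffing pattern". A further model with previous-session dummies is only a test for carry-over. No version without the nicotine covariate is specified.

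Section 5.1 shows where the covariate comes from. The first cigarette of each session is smoked "in a regimented manner: 10 puffs total, 30 seconds between puffs". Afterwards, "The spent cigarette filter will be collected for nicotine analysis". For the three sugar sessions, "The same procedures as implemented with UB cigarettes will be followed".

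The plan also treats nicotine of this kind as an outcome. Section 3.1 sets out "To evaluate the impact of sugar content on smoking intensity (nicotine levels in spent filters), subjective responses to cigarettes". Section 15.1 classes mouth-level nicotine exposure as secondary. Neither place says which of the session's two cigarettes is meant.

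**The concern.** The covariate is not a baseline value. There is one per session, and each is obtained after the participant has smoked the cigarette whose sugar level is under test. The fixed regimen sets the number and spacing of puffs but not puff volume, so it narrows the route from sugar to filter nicotine without closing it. Section 2.0 itself suggests that less sugar could make smoke harsher and harder to inhale.

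If sugar shifts this measure, the adjusted coefficient compares sugar levels at equal first-cigarette nicotine. That is a different quantity from the overall impact in section 15.1. The plan gives no reason for the covariate, declares no direct-effect question, and does not commit to reporting the shift under fixed puffing. A null or a positive primary result could then not be read with confidence as the overall effect of sugar.

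**Working it through.** **Inputs from the plan (sections 15.2 and 15.3).** n = 30 completers; high-low difference d = 0.6; between-session correlation r = 0.50; two-sided alpha 0.025 for each primary outcome.

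**The plan's own power figure.** For a paired comparison:
- SD of the difference = √(2(1 − 0.5)) = 1
- noncentrality = 0.6 × √30 / 1 = 3.29, on 29 df
- power = 0.816, against the stated 0.81

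The other five powers in the section 15.2 table also reproduce to within one percentage point (for example 0.898 against 0.89, and 0.647 against 0.64). The sample size was therefore justified for the difference without the nicotine covariate, which is not the coefficient the primary model estimates.

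**Effect of the covariate.** Let b be the within-condition slope of the outcome on filter nicotine (SD per SD), and g the high-low shift in filter nicotine (SD). In a within-participant linear model:

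adjusted estimate = overall effect − b × g

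This holds whether b is causal or arises from a common cause. With b positive, the estimate is too small if sugar raises filter nicotine and too large if sugar lowers it.

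**Assumptions.** The documents give neither b nor g, so both are varied. The simulation is a three-period crossover with six orders from two Latin squares, n = 30 and 20,000 replicates per setting. Outcome and filter nicotine each have SD 1 and r = 0.5 given condition. Medium sugar lies halfway between low and high, and the overall effect is held at 0.60. The fit is a within-participant regression on condition and session, with and without filter nicotine. Unadjusted power is about 0.83. With the covariate:

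| Shift g (SD) | b = 0.1: estimate, power | b = 0.3: estimate, power | b = 0.5: estimate, power |
|---|---|---|---|
| 0 | 0.60, 0.83 | 0.60, 0.86 | 0.60, 0.93 |
| 0.1 | 0.59, 0.82 | 0.57, 0.82 | 0.55, 0.87 |
| 0.2 | 0.58, 0.80 | 0.54, 0.77 | 0.50, 0.78 |
| 0.4 | 0.56, 0.74 | 0.48, 0.63 | 0.40, 0.54 |
| −0.5 | 0.65, 0.84 | 0.75, 0.95 | 0.85, above 0.99 |

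**One cell by hand (b = 0.3, g = 0.4).**
- Estimate: 0.60 − 0.3 × 0.4 = 0.48
- Within-participant residual variance: 0.5 × (1 − 0.3²) = 0.455
- SE² ≈ 2 × 0.455/30 + 0.4² × 0.455/(56 × 0.5) = 0.0303 + 0.0026 = 0.0329, so SE ≈ 0.181
- The t ratio is about 2.65 against a critical value of 2.30 (55 df), giving power of about 0.63

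**False rejection when the overall effect is zero (nominal 2.5%).** A shift of 0.2 SD gives 3% at b = 0.3 and 5% at b = 0.5. A shift of 0.4 SD gives 6% and 14%. At b = 0.1 it stays at about 3%.

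**Could the planned secondary analysis settle the matter?** Suppose mouth-level nicotine is analysed for the fixed-puff cigarette. The SE of the high-low shift is √(2 × 0.5/30) = 0.18 SD, and the 95% CI half-width is about 2.00 × 0.183 = 0.37 SD. Power at p < 0.05 is 0.08 for a shift of 0.1 SD, 0.19 for 0.2, 0.58 for 0.4 and 0.90 for 0.6. A non-significant result would not show that the adjusted and overall effects agree.

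**Check in a mixed model.** A REML random-intercept fit (400 replicates per setting) at b = 0.3 gave 0.60 and 0.88 with no shift, 0.53 and 0.74 at 0.2 SD, 0.47 and 0.60 at 0.4 SD, and 0.75 and 0.97 at −0.5 SD. This is the same pattern within simulation error.

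**The case against.** The strongest reply is that no bias has been shown. Bias needs both a sugar shift in fixed-puff nicotine and a slope on the outcome, and the documents supply neither. The plan also chose the safer of the two cigarettes, because participants can compensate more freely when smoking ad libitum. Section 3.1 does not say that sugar changes nicotine under fixed puffing. The harshness remark in section 2.0 concerns inhalation, not puff volume or filter deposit. Where the shift is 0.1 to 0.2 SD and the slope 0.1 to 0.3, the estimate is still 0.54 to 0.59, power is 0.77 to 0.82, and false rejection is about 3%. Comparing sugar levels at equal nicotine delivery is also a legitimate question.

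All of this stands as a limit on size. The direction is unknown too. The two endpoints may be affected differently: in each session, "at 30 minutes the Cigarette Purchase Task and Multiple Choice Procedures for the UB cigarettes will be administered" (shown here for the usual-brand session), timed from the later ad libitum cigarette, so the crossover point may depend only weakly on first-cigarette nicotine. At b = 0.1, a 0.2 SD shift moves the estimate by only 0.02.

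The reply does not remove the mismatch. If fixed puffing fully standardised intake, the covariate would serve only precision, and the plan does not say so. A nicotine-controlled comparison needs to be declared, with its assumptions. The planned nicotine outcome is too imprecise to show that the two effects coincide, and it may not cover the fixed-puff cigarette.

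**Conclusion.** The concern holds in conditional form. The sole primary model conditions on a measure taken after the sugar level is assigned, of a kind the plan itself treats as a response to sugar. The aim and the power calculation both refer to the unconditioned effect. Whether the primary result would be distorted, and in which direction, cannot be determined from the documents.

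Under the assumptions above, shifts of 0.1 SD hardly matter. A shift of 0.4 SD with a slope of 0.3 to 0.5 lowers an overall effect of 0.60 to between 0.48 and 0.40, and lowers power from about 0.83 to between 0.63 and 0.54. A shift of −0.5 SD inflates the estimate to between 0.75 and 0.85. This should be fixed before analysis: the harm is uncertain, but the mismatch is plain and the remedy is cheap.

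**What to change.** In section 15.3, make the primary model sugar condition and session with a participant random effect and no filter-nicotine covariate. Keep the nicotine-adjusted model as a labelled secondary analysis of the effect not acting through first-cigarette nicotine intake, and state its assumption of no unmeasured common cause of intake and response. Beside it, report the sugar effect on fixed-puff filter nicotine as an estimate with a 95% CI. Do not choose between the two models by whether that effect is significant.

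The cost is one or two sentences in the analysis plan and no new data. If sugar does not shift filter nicotine, some precision is given up: power is 0.83 rather than 0.86 at a slope of 0.3, or rather than 0.93 at a slope of 0.5, with no loss at 0.1.

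### The session-1 usual-brand value is left out of the primary model as already adjusted for; with incomplete sessions and a session-level nicotine covariate that is not exact, and adding it is a small, free gain

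*Combined protocol and SAP*

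**What the plan says.** Section 15.3 (Primary Analysis) specifies a linear mixed model with sugar condition and session as within-subject factors, "adjusted for the nicotine levels in spent filters of the first study cigarette used in each of the laboratory sessions". The usual-brand measure from session 1 and the other participant-level factors are described as "naturally adjusted across different sugar conditions because of the within-subject design, and hence are not included in the model".

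The missing-data text in the same section states: "All observed data will be utilized in the analyses, with missing data being assumed to be missing at random, by using the mixed effects models". It also says: "We will compare subjects who do and do not complete the study sessions in terms of their baseline characteristics". No model change or sensitivity analysis is tied to that comparison.

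On how much loss to expect, Section 15.3 says: "We anticipate a high retention rate (>80%) because of the short period of time of this laboratory study". Section 5.1 says: "Anticipating a 60-65% attrition rate based on current experiences", with up to 75 recruited for 30 completers.

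Under Section 5.1, session 1 is the usual-brand session for everyone. It collects the mCEQ and the Multiple Choice Procedure, which supply the two primary outcomes. The three study-cigarette sessions then follow the same procedures. So anyone who contributes study-cigarette data has already attended the session that measures the usual-brand value.

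**The concern.** The stated reason for the omission is cancellation. When each participant is observed under all three sugar levels, a quantity that is constant within the participant has no effect on the comparison of levels. The plan does not confine itself to that case. It keeps participants with one or two study sessions, and for them a mixed model also draws on differences between participants, where the usual-brand value does not cancel. The session-level nicotine covariate breaks exact cancellation as well, even when nobody drops out.

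Missing at random, as this model uses it, conditions on what the model contains. If leaving depends partly on how the study cigarette compared with the usual brand, the model ignores an observed value that carries information about who left. What is at stake is some attenuation of the sugar effect, or some lost precision. The plan's own power is 0.81 at the target and 0.64 at d = 0.5.

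**Working it through.** **1. The plan's own figure.** Inputs from Section 15.2: n = 30, d = 0.6, r = 0.5, two-sided alpha 0.025. For a single contrast, Hotelling's T² is the paired t test, that is, F(1, 29) with noncentrality n·d²/[2(1 − r)] = 30 × 0.36 / 1.0 = 10.8. Power is 0.816, against 0.81 stated. The other five rows give 0.898, 0.647, 0.754, 0.923 and 0.968, against 0.89, 0.64, 0.75, 0.92 and 0.96. The planning model is reproduced.

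**2. Why cancellation is not exact.** Take unit outcome variance and r = 0.5, so that the between-participant and residual variances are each 0.5. A high-low difference within one participant has variance 2 × 0.5 = 1.0 and contains no participant constant. A high-low difference between two participants with one session each has variance 2 × (0.5 + 0.5) = 2.0 and contains both constants. The mixed model gives the second kind lower weight, but not zero weight.

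**3. Size of the effect.** The three-session crossover was simulated and fitted by REML with a random intercept, with and without the usual-brand value. From the plan: session correlation 0.5 and high-low effect 0.6. Assumed, because the documents give no figures:
- medium-level effect 0.3;
- correlation of usual brand with study sessions 0.5 or 0.65;
- log-odds of dropout changing by 1.5 per SD;
- three or six sequences;
- no nicotine term in these runs.

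Bias in the high-low contrast (SD units, true value 0.6, large samples):

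| Dropout depends on | Retained to session 4 | Without usual brand | With usual brand |
|---|---|---|---|
| nothing (complete data) | 100% | 0.00 | identical |
| usual brand alone | 77% and 42% | 0.00 | 0.00 |
| usual brand minus last session's value | 81-83% | −0.01 | within 0.003 |
| usual brand minus last session's value | 46% | −0.01 to −0.02 | within 0.003 |
| usual brand, after the low-sugar session | 74-82% | −0.01 to −0.04 | within 0.003 |
| usual brand, after the low-sugar session | 30-37% | −0.03 to −0.07 | within 0.003 |

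As a share of the design effect, 0.01/0.6 = 2%, 0.04/0.6 = 7% and 0.07/0.6 = 12%. A separate check with the variances treated as known gave average estimates of about 0.59 near 80-90% retention and 0.56-0.58 at 42-45%, and about 0.60 with the covariate.

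The second row is unbiased because order is independent of the usual-brand value. Selective loss then shifts the session-4 effect (by −0.06 to −0.22 without the covariate) but falls evenly on the three sugar levels.

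**4. Precision when dropout depends on usual brand alone.** With usual-brand correlation 0.5, the model standard error goes from 0.177 to 0.176 at n = 38 (30/0.8, rounded up) and from 0.154 to 0.149 at n = 75 with 42% retention, a fall of about 1% and 3%. With correlation 0.65 the changes are 0.178 to 0.174 and 0.155 to 0.145, about 2% and 6%.

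**5. Complete data with a session-level nicotine covariate.** In 300 simulated trials of n = 30, adding usual brand moved individual estimates by SD 0.018 (maximum 0.08), with mean shift about 0. Without the nicotine term the two analyses agreed to rounding error.

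**The case against.** The case for leaving the plan alone is a reasonable one. A participant with two study sessions still supplies a within-person contrast free of any constant. Only the recovered between-participant information carries the usual-brand value, and counterbalancing protects the sugar contrast when dropout depends on that value alone. Observed ratings are already in the likelihood. Nothing in the documents says that usual-brand ratings, or a shortfall against them, drive dropout. The overnight abstinence and CO requirement at each session is at least as plausible a cause, and the session payments and completion bonus work against leaving. The completer comparison is a partial safeguard. At the retention Section 15.3 expects, a bias of 0.01-0.04 SD is below a quarter of the standard error of about 0.17-0.18 at n = 38. All of this stands. It limits the size of the point but does not make the stated justification exact.

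Three stronger readings are tempting, and the documents do not support them:
- *Any incomplete data bias the sugar contrast.* They do not. Dropout must depend on the usual-brand value jointly with a session's rating or sugar level.
- *The 60-65% attrition is loss among people already smoking study cigarettes.* Section 10.1 counts up to 75 from consent, and (75 − 30)/75 = 60%. Section 15.2 speaks of eligible smokers enrolled, which leaves some ambiguity, but much of the loss may come before session 2. Those people supply no study-cigarette data, so the covariate cannot help with them.
- *Adding the covariate changes nothing when data are complete.* That is true only without the nicotine term, which the plan includes.

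**Conclusion.** The point holds as a free improvement, not as a threat to the trial. The justification for omitting the usual-brand value is approximately right for the sugar contrast, but it is not exact for the model and data the plan describes. The likely cost of the omission lies between a slightly larger standard error and attenuation of about 0.01-0.04 SD near 80% retention of those starting session 2. The figure of about 0.07 SD needs retention near 30%, which no section states for participants who have begun study cigarettes.

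The bias figures rest on an assumed dropout mechanism of considerable strength and on a random-intercept structure, which Section 15.3 does not spell out. A reader might infer that the usual-brand value is a known predictor of dropout; the documents give no evidence either way. No scenario examined would by itself overturn the trial's conclusion.

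**What to change.** Pre-specify the participant's session-1 usual-brand value of the same outcome, taken at the matching point in the session, as a covariate in the primary mixed model for each of the two primary outcomes. Replace the sentence that justifies omitting it with a statement that the usual-brand value is included because cancellation is not exact when sessions are missing or when a session-level nicotine covariate is in the model.

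The cost is one model term, one degree of freedom and one sentence, with no new data or visits. It should be written in before outcome data are examined, because adding the covariate after seeing who dropped out would look data-driven.
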